## **11.2 Record maintenance and retention**

The Sponsor-Investigator will maintain records in accordance with Good Clinical Practice guidelines; to include:

- FDA correspondence related to the IND and clinical protocol, including copies of submitted Safety Reports and Annual Reports
- IRB correspondence (including approval notifications) related to the clinical protocol; including copies of adverse event reports and annual or interim reports
- Current and past versions of the IRB-approved clinical protocol and corresponding IRB-approved consent form(s) and, if applicable, subject recruitment advertisements
- Signed FDA Form 1572 Statements of Investigator (i.e., for the Sponsor-Investigator)
- Financial disclosure information (i.e., for the Sponsor-Investigator and for sub-investigators who will be involved in the administration of the study drugs and/or the evaluation of research subjects [i.e., who will contribute significantly to the research study data])
- Curriculum vitae (i.e., for the Sponsor-Investigator)
- Certificates of required training; e.g., human subject protections, Good Clinical Practice, etc. (i.e., for the Sponsor-Investigator and for all sub-investigators who will be involved in the administration of the study drugs and/or the evaluation of research subjects [i.e., who will contribute significantly to the study data])
- Listing of printed names/signatures. (i.e., for the Sponsor-Investigator and for all sub-investigators who will be involved in the administration of the study drugs and/or the evaluation of research subjects [i.e., who will contribute significantly to the study data])
- Normal value(s)/range(s) for medical/laboratory/technical procedures or tests included in the clinical protocol
- Laboratory certification information
- Instructions for on-site preparation and handling of the investigational drug(s), study treatment(s), and other study-related materials (i.e., if not addressed in the clinical protocol)
- Responsibility delegation log
- Signed informed consent forms

- Completed Case Report Forms; signed and dated by Sponsor-Investigator
- Source Documents or certified copies of Source Documents
- Monitoring visit reports
- Copies of Sponsor-Investigator correspondence (including notifications of safety information) to sub-investigators
- Subject screening and enrollment logs
- Subject identification code list
- Investigational drug accountability records, including documentation of drug disposal.
- Final clinical study report
- Decoding procedures for blinded trials
- Master randomization list
- Signed FDA Form 1572 Statements of Investigator (i.e. for Investigators responsible for the conduct of the clinical research study at external study sites).
- Financial disclosure information (i.e., for Investigators responsible for the conduct of the clinical research study at external study sites; also for all study site sub-investigators who will be involved in the administration of the study drugs and/or the evaluation of research subjects [i.e., who will contribute significantly to the study data])
- Curriculum vitae (i.e., for Investigators responsible for the conduct of the clinical research study at external study sites)
- Certificates of required training; e.g., human subject protections, Good Clinical Practice, etc. (i.e., for Investigators responsible for the conduct of the clinical research study at external study sites; also for all study site sub-investigators who will be involved in the administration of the study drugs and/or the evaluation of research subjects [i.e., who will contribute significantly to the study data])
- Listing of printed names/signatures (i.e., for Investigators responsible for the conduct of the clinical research study at external study sites; also for all study site sub-investigators who will be involved in the administration of the study drugs and/or the evaluation of research subjects [i.e., who will contribute significantly to the study data])
- Copies of initial and continuing IRB approval notifications (i.e., for each of the external study sites)
- Normal value(s)/range(s) for medical/laboratory/technical procedures or tests included in the clinical protocol (i.e., for each of the external study sites)
- Laboratory certification information (i.e., for each of the external study sites)
- Monitoring visit reports (i.e., for all external study sites)
- Copies of Sponsor-Investigator correspondence (including notifications of safety information) to Investigators responsible for the conduct of the clinical research study at external study sites

The Sponsor-Investigator will retain the specified records and reports for up to 2 years after the marketing application is approved for the investigational drug; or, if a marketing application is not submitted or approved for the investigational drug, until 2 years after investigations under the IND have been discontinued and the FDA so notified.

## **12. Ethics:**

### **12.1      Institutional Review Board (IRB) approval**

The Sponsor-Investigator will obtain, from the University of Pittsburgh Institutional Review Board (IRB), prospective approval of the clinical protocol and corresponding informed consent form(s); modifications to the clinical protocol and corresponding informed consent forms, and advertisements (i.e., directed at potential research subjects) for study recruitment.

The only circumstance in which a deviation from the current IRB-approved clinical protocol/consent form(s) may be initiated in the absence of prospective IRB approval is to eliminate an apparent immediate hazard to the research subject(s). In such circumstances, the Sponsor-Investigator will promptly notify the University of Pittsburgh IRB of the deviation.

The University of Pittsburgh IRB operates in compliance with FDA regulations at [21 CFR Parts 50](#) and [21 CFR 56](#), and in conformance with applicable International Conference on Harmonization (ICH) Guidelines on Good Clinical Practice (CGP).

In the event that the University of Pittsburgh IRB requires, as a condition of approval, substantial changes to a clinical protocol submitted under an FDA-accepted IND application, or in the event of the Sponsor-Investigator's decision to modify the previously accepted clinical protocol:

- For a Phase 1 clinical study: The Sponsor-Investigator will submit (i.e., in advance of implementing the change) a Protocol Amendment to the IND describing any change to the Phase 1 clinical protocol that significantly affects the safety of the subjects. For changes that do not affect critical safety assessments, the revisions to the clinical protocol will be addressed in the Annual Report to the IND.
- For Phase 2 and 3 clinical studies: The Sponsor-Investigator will submit (i.e., in advance of implementing the change) a Protocol Amendment to the IND describing any change to a Phase 2 or Phase 3 protocol that significantly affects the safety of subjects, the scope of the investigation, or the scientific quality of the study. Examples of Phase 2 and 3 clinical protocol changes requiring the submission of a Protocol Amendment include:

- Any increase in drug dosage or duration of exposure of individual subjects to the investigational drug beyond that described in the current protocol, or any significant increase in the number of subjects under study.
- Any significant change in the design of the protocol (such as the addition or deletion of a control group).
- The addition of a new test or procedure that is intended to improve monitoring for, or reduce the risk of, a side effect or adverse event; or the dropping of a test intended to monitor the safety of the investigational drug.

## **12.2 Ethical and scientific conduct of the clinical research study**

The clinical research study will be conducted in accordance with the current IRB-approved clinical protocol; ICH GCP Guidelines adopted by the FDA; and relevant policies, requirements, and regulations of the University of Pittsburgh IRB, University of Pittsburgh and UPMC, Commonwealth of Pennsylvania, and applicable federal agencies.

## **12.3 Subject informed consent**

The Sponsor-Investigator will make certain that an appropriate informed consent process is in place to ensure that potential research subjects, or their authorized representatives, are fully informed about the nature and objectives of the clinical study, the potential risks and benefits of study participation, and their rights as research subjects. The Sponsor-Investigator, or a sub-investigator(s) designated by the Sponsor-Investigator, will obtain the written, signed informed consent of each subject, or the subject's authorized representative, prior to performing any study-specific procedures on the subject. The date and time that the subject, or the subject's authorized representative, signs the informed consent form and a narrative of the issues discussed during the informed consent process will be documented in the subject's case history. The Sponsor-Investigator will retain the original copy of the signed informed consent form, and a copy will be provided to the subject, or to the subject's authorized representative.

The Sponsor-Investigator will make certain that appropriate processes and procedures are in place to ensure that ongoing questions and concerns of enrolled subjects are adequately addressed and that the subjects are informed of any new information that may affect their decision to continue participation in the clinical study. In the event of substantial changes to the clinical study or the risk-to-benefit ratio of study participation, the

Sponsor-Investigator will obtain the informed consent of enrolled subjects for continued participation in the clinical study

### **13. Study Discontinuation Criteria:**

#### **13.1 Discontinuation of individual research subjects (refer also to sections 5.1.1 and 8.4)**

Because we are interested in evaluating efficacy, we will use a per-protocol approach, as opposed to an intention-to-treat approach for the conduct of this study. As such, subjects that are non-compliant with the medication regimen (defined as taking less than 80% of the medication doses) will be withdrawn from the study and additional subjects will be recruited to replace subjects that have been withdrawn due to non-compliance. Subjects that are withdrawn for non-compliance will be instructed to terminate administration of the study medication without tapering down the dose and to return unused medication to the investigators.

As specified in section 8.4 subjects with symptomatic hypotension or abnormal lab values will be withdrawn from study participation. Additionally, females that become pregnant while taking the study medication will immediately stop the medication and will be withdrawn from the study. These withdrawn subjects will be followed clinically based on standards of care until the adverse event or abnormal test findings felt to be associated with the study drug resolve or stabilize at a level satisfactory to the Sponsor-Investigator, however no further research data will be collected once the subject has been withdrawn.

Subjects that are withdrawn due to non-compliance with the study medication, symptomatic hypotension, abnormal lab values or pregnancy will be reported as an adverse event. Withdrawn subjects will be replaced by recruiting another subject to take the place of the withdrawn subject.

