## **5. Study Drug(s):**

As described in section 1.2, losartan potassium is an FDA-approved drug for the treatment of hypertension, left ventricular hypertrophy and diabetic nephropathy. It is prescribed for oral intake at doses from 25-100 mg per day with a usual starting dose of 50 mg per day which is what will be used for this study. Losartan potassium was developed by Merck under the proprietary name Cozaar® and is now generically available.

Prior to starting the study medication, a study physician will review the effects of losartan, its side-effects and how the medication should be taken with all subjects. At this time, the physician will answer any questions the subject has regarding the study medication. Subjects will be evaluated weekly while they are taking the medication. Blood work will be repeated 2, 4 and 6 weeks after randomization to identify any clinically relevant abnormalities.

Following randomization, subjects will begin a closed label course of 50mg of Losartan daily for 4 weeks or placebo for the same duration of time. Losartan will be initiated within 7 days of injury after initial tests are performed and any abnormalities are ruled out. No initial dosage adjustment is necessary. The drug will be self-administered by the subject with or without food and will be ingested once a day. With the dose that will be used in this study, no tapering is necessary at the end of the intervention phase or if the subject needs to be withdrawn from the study.

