### **5.1.1 Withdrawal of subjects due to non-compliance/adherence**

Because we are interested in evaluating efficacy, we will use a per-protocol approach, as opposed to an intention-to-treat approach for the conduct of this study. As such, subjects that are non-compliant with the medication regimen (defined as taking less than 80% of the medication doses) will be withdrawn from the study and additional subjects will be recruited to replace subjects that have been withdrawn due to non-compliance. Subjects that are withdrawn for non-compliance will be instructed to terminate administration of the study medication without tapering down the dose and to return unused medication to the investigators.

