**Specific Aim #2: Recovery of Hamstring Muscle Function and Structure**

The primary endpoints to assess hamstring muscle function are the injured to contra-lateral leg differences in the popliteal angle at 6 weeks and 6 months and the injured to contra-lateral ratio of peak isokinetic hamstring torque at 6 weeks and 6 months.

The primary endpoint to assess hamstring structure will be the length and volume of fibrosis within the hamstrings at 6 months as evidence on 3 Tesla MRI.

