## **9.2        Sample size determination**

With an approved sample size of 20 patients (10 in each group), we will not have enough statistical power to detect statistically significant differences in clinical measures between the Losartan and placebo groups. Therefore the objective of this phase 1 trial is to observe trends by group and estimate effect sizes that can be used to inform power calculations in future clinical trials.

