## **9.3        Definition(s): Analysis population(s)**

All analyses for treatment group comparisons will use the original treatment assignment as randomized for each participant (intent-to-treat) regardless of the subject's actual compliance with taking the study medications. Secondary analyses will consider per protocol analysis, in which compliance with the study medication regimen will be defined as taking greater than 80% of the doses.

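### Sections 5.1.1 and 13.1 reject intention-to-treat and withdraw and replace non-adherent subjects, which undercuts the intent-to-treat analysis set in 9.3

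*Combined protocol and SAP*

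**What the plan says.** **Conduct rules.** Sections 5.1.1 and 13.1 carry the same sentence: "we will use a per-protocol approach, as opposed to an intention-to-treat approach for the conduct of this study". The reason given is an interest in efficacy. It follows that "subjects that are non-compliant with the medication regimen (defined as taking less than 80% of the medication doses) will be withdrawn from the study", and that "additional subjects will be recruited to replace subjects that have been withdrawn due to non-compliance". Section 13.1 also counts withdrawal for non-compliance as an adverse event.

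**Analysis rule.** Section 9.3 states: "All analyses for treatment group comparisons will use the original treatment assignment as randomized for each participant (intent-to-treat", and adds that compliance makes no difference to this. It continues: "Secondary analyses will consider per protocol analysis", with compliance meaning more than 80% of doses.

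**Safety withdrawals.** Section 8.4 ends study appointments for a subject terminated for an adverse event and replaces that subject. Section 13.1 ends research data collection after withdrawal for symptomatic hypotension, abnormal laboratory values or pregnancy.

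**Timing and purpose.** Under Section 5, "subjects will begin a closed label course of 50mg of Losartan daily for 4 weeks", or take placebo for the same time. Table 1 reviews medication logs at weeks 1 to 4 only. The primary function endpoints in 9.1.1 include "injured to contra-lateral leg differences in the popliteal angle at 6 weeks and 6 months", and the isokinetic torque ratio at the same two times. The MRI endpoint is at 6 months, and recurrence runs to 12 months. Section 9.2 disclaims power and aims to "estimate effect sizes that can be used to inform power calculations in future clinical trials".

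**The concern.** An intent-to-treat comparison needs outcomes from everyone randomised, including those who stop taking the tablets. The conduct rules take those subjects out at or before about week 4, ahead of nearly every primary efficacy endpoint. For outcomes after week 4, the intent-to-treat and per-protocol sets would then contain almost the same subjects, and the distinction in 9.3 loses its purpose.

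Adherence is decided after randomisation and may depend on side effects or on how recovery is going. A replacement restores the head count but not the randomised comparison. Since the trial claims no power, the efficacy aims deliver effect estimates for planning a later trial, and those estimates should come from a defined and complete set. The first aim, safety, is also touched in two ways. Later safety data on withdrawn subjects may be missing. And missed tablets, once recorded as adverse events, would enter the Fisher exact comparisons in 9.5.

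**Working it through.** The plan has no figure to reproduce: 9.2 takes 20 subjects (10 per group) as given and derives it from no power calculation. The check is a comparison of sections, followed by an illustration of size.

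**Step 1. The sections side by side**

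| | 5.1.1 and 13.1 | 9.3 |
|---|---|---|
| Approach named | Per-protocol; intention-to-treat rejected by name | Intent-to-treat for all group comparisons |
| Non-adherent subject | Withdrawn and replaced | Kept in the arm assigned |
| Per-protocol | The study's approach | Secondary |
| Threshold | Under 80% is non-compliant | Over 80% is compliant |

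The threshold wording is not part of the conflict. Four weeks of daily dosing is 4 × 7 = 28 doses, and 0.80 × 28 = 22.4. Under both wordings 23/28 = 82.1% is compliant and 22/28 = 78.6% is not. Exactly 80% cannot occur.

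**Step 2. What a subject withdrawn by week 4 would lack**

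- Popliteal angle: the 6-week and 6-month values. Baseline and weekly values up to withdrawal exist.
- Isokinetic torque: both endpoint values. Table 1 has no earlier test (6.4.2.2 also mentions one at week 4).
- MRI: the 6-month scan.
- Days to return to practice: missing if return comes after withdrawal.
- Recurrence: everything from withdrawal to 12 months.
- Aim 1: the week-6 laboratory values and later adverse events. Section 8.4 does provide blood work 4 to 6 weeks after the drug stops, as clinical follow-up, but 13.1 ends research data collection for safety withdrawals.

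**Step 3. How likely it is.** The documents give no adherence rate. For an assumed non-adherence rate d:

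| d | Chance of at least one in 20: 1 − (1 − d)^20 | Randomised to keep 20 adherent: 20/(1 − d), rounded up |
|---|---|---|
| 5% | 64% | 22 |
| 10% | 88% | 23 |
| 20% | 99% | 25 |

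**Step 4. Share of all randomised without later outcomes** after k replaced withdrawals, k/(20 + k): 1/21 = 4.8%, 2/22 = 9.1%, 3/23 = 13.0%. Section 9.4 anticipates under 5% loss at 6 months. One withdrawal fits within that and two do not, though the figure may not have been meant to cover withdrawals that the protocol itself orders.

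**Step 5. Possible bias if all k fall in one arm of 10.** The plan does not say which arm a replacement enters, so both cases are shown. Share missing: k/(10 + k) if the replacement enters the same arm, k/10 if it enters the other. Shift in the arm mean = share × assumed difference of 1 SD between withdrawn and remaining subjects.

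| k | Same arm | Other arm | Shift | Shift as a share of one standard error |
|---|---|---|---|---|
| 1 | 1/11 = 9.1% | 1/10 = 10% | 0.09 to 0.10 SD | 20% to 22% |
| 2 | 2/12 = 16.7% | 2/10 = 20% | 0.17 to 0.20 SD | 37% to 45% |

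The standard error of the group difference with 10 per arm is √(1/10 + 1/10) = 0.447 SD. The shift is proportional to the assumed difference. At 0.5 SD the k = 2 row halves to 0.08 to 0.10 SD; at 2 SD it doubles to 0.33 to 0.40 SD, still below one standard error.

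**The case against.** The strongest defence is that 5.1.1 and 13.1 concern conduct and 9.3 concerns analysis. Much of this stands. A reader might infer that the plan has two rival primary analyses, and the documents do not support that. The per-protocol sentence sits under headings on withdrawal and discontinuation, and neither section defines an analysis set. Section 9.3 does, for all group comparisons, and a statistician would follow it. The defence does not remove the problem, however: the conduct rules take away data that the 9.3 analysis needs.

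A reader might also infer that 13.1 expressly ends data collection for non-compliant subjects. It does not. That clause follows, and refers to, the withdrawals for hypotension, laboratory values and pregnancy. For non-compliance the loss is inferred from withdrawal plus replacement, with no follow-up provided anywhere. That is the natural reading, but it is not a stated rule.

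Section 9.4 deserves credit. Its mixed models can use a withdrawn subject's earlier popliteal angles under the original assignment. The comparison of drop-outs and the good-score/poor-score sensitivity analysis describe and bound the loss. None of these recovers torque, MRI or recurrence.

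Finally, aligning 9.3 with 5.1.1 would also end the contradiction, so choosing intention-to-treat is a design decision. It is the better one, because it preserves the randomised comparison and the plan already assigns per-protocol a secondary role.

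**Conclusion.** The point holds in this form: 5.1.1 and 13.1 conflict in words with 9.3, and the withdrawal and replacement rules would leave the operative intent-to-treat analysis incomplete. No section reconciles them. The textual conflict is certain. Loss of data is explicit for safety withdrawals and inferred for non-compliance.

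The size is modest. Under the assumptions that one or two withdrawals fall in a single arm and differ from the rest by 1 SD, the bias is less than half of one standard error. The number of withdrawals is unknown. This should be corrected, mainly because it is cheap and the trial's product is its estimates and safety record. It does not threaten the trial, and a claim of serious bias would go beyond the documents.

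**What to change.** 1. In 5.1.1 and 13.1, delete the sentence choosing per-protocol over intention-to-treat. State that non-adherent subjects are neither withdrawn nor replaced and are followed to 12 months.
2. In 9.3, use adherence only to define the secondary per-protocol set, from the week-4 pill count: at least 23 of 28 doses.
3. In 13.1, remove non-compliance from the withdrawals reported as adverse events, so that missed doses do not enter the Fisher tests in 9.5.
4. In 8.4 and 13.1, for safety stops: stop the drug, but continue outcome and safety follow-up where the subject agrees and the study physician judges each procedure medically suitable. The condition matters because follow-up includes maximal isokinetic testing and MRI, and these subjects may be hypotensive or pregnant.
5. In 9.3, keep subjects stopped for safety in the intent-to-treat set under their original assignment even if a replacement is recruited. Do not label them non-compliant solely because the drug was stopped; someone stopped at week 2 can have taken at most 14/28 = 50% of doses.

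The cost is a few sentences in four sections. Pill counts are already collected. Not replacing non-adherent subjects adds no recruitment, and safety stops add a few visits for the subjects concerned. The downside is that the per-protocol set may be smaller than 20, which is acceptable for a secondary analysis.

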#### **8.4 Withdrawal of subjects due to adverse events**

Vital signs, including blood pressure and heart rate will be monitored daily prior to each rehabilitation session. Individuals with symptomatic hypotension (defined as symptoms consistent with hypotension including dizziness, lightheadedness etc. with systolic or diastolic blood pressure less than 90 and 60 mm Hg respectively) will be discontinued from the study. Withdrawal of a subject due to symptomatic hypotension will be reported as an adverse event.

Blood work, including a chemistry panel with electrolytes and complete blood cell count (CBC) will be performed prior to randomization and at 2, 4, and 6 weeks after randomization. The blood work will be used to assess hemoglobin and hematocrit counts, serum potassium and uric acid levels, liver function (alanine aminotransferase (ALT), aspartate aminotransferase (AST) and alkaline phosphatase), renal function (blood urea nitrogen [BUN] and serum creatinine), creatine phosphokinase (CPK) to assess muscle injury, and pregnancy in women (human chorionic gonadotropin (hCG)). Additional blood work will be ordered if subjects report new fatigue, peripheral edema or urinary symptoms. Follow-up blood work will be performed 4-6 weeks ( $\pm 3$  days) after discontinuing medication to ensure that lab values have returned to normal ranges after discontinuation of the study medication. Abnormal lab values resulting in subject withdrawal from the study will be reported as an adverse event.

Human chorionic gonadotropin (hCG) be determined to identify pregnant women will be assessed prior to randomization and at 2, 4 and 6 weeks after randomization. Women that are pregnant prior to randomization will be discontinued from the study, but will not be reported as an adverse event.

Human chorionic gonadotropin will also be determined for females enrolled in the study who expect that they For females enrolled in the study that have become pregnant, the study medication will be stopped immediately and the subject will be withdrawn from the study. Pregnancy necessitating withdrawal from the study will be reported as an adverse event.

Adverse events or abnormal test findings felt to be associated with the study drug(s) will be followed until the event (or its sequelae) or the abnormal test finding resolves or stabilizes at a level acceptable to the Sponsor-Investigator.

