The severity of an adverse event will be determined by the study medical director based on the criteria stated in section 8.1. Additionally, the medical director will assign the event a grade of mild, moderate, or severe. If it becomes medically necessary to withdraw the subject from the study, the study medication will be discontinued. The subject will be followed clinically until the adverse event or abnormal test findings felt to be associated with the study drug resolves or stabilizes at a level acceptable to the Sponsor-Investigator. This follow-up will include assessment of vital signs, physical examination and assessment of blood work. Follow-up blood work will be performed 4-6 weeks ( $\pm 3$  days) after discontinuing medication to ensure that lab values have returned to normal ranges after discontinuation of the study medication. The subject will be treated for any medication related problems as clinically appropriate. Information from this appointment will be documented in the subject's case file. The patient will be terminated from the study, and will not complete any further follow-up appointments for the study. Subjects that are terminated from participation in the study due to an adverse event will be replaced by recruitment of another subject.

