## **9.4        Effectiveness analysis**

The distribution of baseline characteristics and important prognostic factors (age, sex, body mass index, pre-injury activity level, etc) will be summarized overall, and by treatment (versus control) group to assess the effectiveness of the randomized allocation. Continuous variables will be summarized with means and standard deviations, and medians and inter-quartile ranges. Categorical data will be summarized using frequencies and percentages. We will then graphically explore the distributions of the primary outcome variables (for normality or skewedness and potential outliers) using q-q plots and histograms before conducting any tests to compare the two groups. When appropriate, transformations will be applied to outcome measures that are not normally distributed.

We anticipate minimal loss to follow-up (<5% of patients) at the 6 month assessment and only 10-15% loss to follow-up at 12 months post-injury. The primary outcome measures (safety and tolerance, recovery of muscle structure and function, return to prior level of function) will be evaluated between 6 weeks and 6 months; therefore the only outcome that could appreciably be affected by lost to follow-up is recurrence of injury within 12 months. We will compare baseline characteristics between participants and drop-outs, obtain reasons for

study drop (to investigate the possible missing data mechanism), and will also conduct a sensitivity analysis (assigning poor scores and good scores to those persons with missing information differentially by treatment assignment) to evaluate the impact on our study results.

For outcome variables that are measured repeatedly, we will use mixed models to adjust for correlation among the observations from the same person as well as a clustering effect for each site. In these models, subject characteristics such as age, sex, and treatment group will be fixed effect predictors, and subject and site identification will be included as random effects. Depending on the type of outcome variable of interest, we will employ linear mixed models or mixed effect logistic regression. Though we do not anticipate statistically significant differences between the Losartan and placebo groups due to the small sample size, these analyses will guide us in developing future clinical trials.

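### Sections 5.1.1, 8.4 and 13.1 treat stopping study drug as leaving the study and replace the subject, which conflicts with the as-randomised analysis in section 9.3

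*Combined protocol and SAP*

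**What the plan says.** Section 13.1 states that "subjects with symptomatic hypotension or abnormal lab values will be withdrawn from study participation", and it treats pregnancy during dosing the same way. For these subjects clinical follow-up continues until the finding resolves or stabilises, but "no further research data will be collected once the subject has been withdrawn". It then adds: "Withdrawn subjects will be replaced by recruiting another subject to take the place of the withdrawn subject".

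Section 8.4 leads to the same place for a medically necessary withdrawal: "The patient will be terminated from the study, and will not complete any further follow-up appointments for the study", and "Subjects that are terminated from participation in the study due to an adverse event will be replaced by recruitment of another subject". On laboratory findings it is conditional: "Abnormal lab values resulting in subject withdrawal from the study will be reported as an adverse event".

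Section 5.1.1, repeated at the start of 13.1, withdraws and replaces anyone taking less than 80% of doses. Both places justify this by declaring that the study is conducted per protocol and not by intention to treat.

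Section 9.3 takes the opposite position: "All analyses for treatment group comparisons will use the original treatment assignment as randomized for each participant (intent-to-treat", whatever the compliance, with per protocol as a secondary analysis. For missing data, section 9.4 plans a comparison of drop-outs with participants, mixed models for repeated outcomes, and a sensitivity analysis "assigning poor scores and good scores to those persons with missing information differentially by treatment assignment".

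**The concern.** The protocol has one action where it needs two. Stopping study drug protects the subject. Leaving the study ends outcome collection. The withdrawal sections merge them, so an event that justifies the first also causes the second.

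These events occur after randomisation and may depend on treatment. Section 1.2 lists changes in potassium, uric acid, liver and renal function among reported losartan effects, and hypotension is among the safety outcomes. Outcomes would then be missing for a reason that can differ between arms, and replacements would refill the arms with subjects who had no such event.

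No powered test is at stake. Section 9.2 says that the trial exists to show trends and estimate effect sizes for planning a later trial. Those estimates would describe a selected group and not the group randomised. Aim 1 is touched too. Section 8.2.1 elicits adverse events at scheduled visits and calls to 12 months, and that systematic questioning stops at withdrawal even though clinical follow-up of the triggering event goes on.

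**Working it through.** There is no power calculation to reproduce: section 9.2 gives 20 subjects (10 per group) as an approved size. The check is a comparison of texts and a count.

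**Texts side by side**

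- Sections 5.1.1 and 13.1: conduct is per protocol, and non-compliant subjects are withdrawn and replaced.
- Sections 8.4 and 13.1: subjects withdrawn for laboratory values, hypotension or pregnancy have no further research data collected and are replaced.
- Section 9.3: all comparisons are as randomised, regardless of compliance.

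Keeping a withdrawn subject in the assigned arm would satisfy 9.3 on paper, but the outcomes would still be absent. The plan does not say how a replacement enters the as-randomised set.

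**What one laboratory withdrawal loses**

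Inputs:
- First dose on Day 0 (Table 1) and daily dosing for 4 weeks (section 5): 4 × 7 = 28 doses.
- Post-randomisation draws at weeks 2, 4 and 6 (section 3.1).
- Contacts after Day 0 (Table 1, activity-level row): weeks 1, 2, 3, 4, 6 and 12, and months 4, 6, 9 and 12, giving 10.
- Primary Aim 2 measurements (section 9.1.1): popliteal angle at 6 weeks and 6 months, torque ratio at 6 weeks and 6 months, fibrosis length and volume at 6 months, giving 2 + 2 + 2 = 6.
- Recurrence followed for 12 months, taken as 52 weeks.

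| Triggering draw | Doses left to stop | Contacts lost | Primary Aim 2 measurements lost | Recurrence weeks unobserved |
|---|---|---|---|---|
| Week 2 | 28 − 14 = 14 at most | 8 of 10 | 6 of 6 | 52 − 2 = 50 |
| Week 4 | 28 − 28 = 0 | 6 of 10 | 6 of 6 | 52 − 4 = 48 |
| Week 6 | 0 | 5 of 10 | 4 of 6 | 52 − 6 = 46 |

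The week-6 row assumes that the 6-week tests are completed at the same visit as the draw. Two of the three draws therefore fall at or after the end of dosing.

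**Share of the trial**

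One withdrawal is 1/10 = 10% of an arm and 1/20 = 5.0% of the trial (1/21 = 4.8% if the replacement is counted). Two are 2/20 = 10% (2/22 = 9.1%). Section 9.4 expects under 5% loss at 6 months and reasons that only recurrence could be appreciably affected. It does not say whether withdrawals under the protocol's own rules are in that figure. If they are, one or two cases use it up, and the losses include the 6-month function and MRI endpoints.

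**Under the fix**

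If the trigger stopped drug only, outcomes lost by rule would be 0 of 20.

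**The case against.** Withdraw-and-replace for non-compliance is a declared choice and not an oversight. That is correct, and it explains the rule. It does not remove the contradiction, because section 9.3 makes the opposite choice for all group comparisons.

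A reader might infer from 13.1 that any out-of-range value at week 4 or 6, including a CPK raised by the injury itself, must end participation. The documents do not support that. Section 13.1 refers back to 8.4, which speaks of values that result in withdrawal and of medical necessity, and whose wording on discontinuing medication suggests a subject still on drug. CPK is listed as a measure of muscle injury and is nowhere named as a withdrawal trigger. What stands is narrower: no section limits the rule to the dosing period, so its reach at those draws is unclear.

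The events may be rare. Subjects are 18 to 35 years old, without diabetes or cardiovascular, renal or hepatic disease, and take a usual starting dose for four weeks. Zero laboratory withdrawals is compatible with everything in the protocol.

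Section 9.4 does offer some protection. The mixed models use repeated measurements made before withdrawal, and the good/poor-score analysis bounds the effect of what is missing. Neither can recover a 6-month MRI or 12-month recurrence status that was never observed.

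**Conclusion.** The conflict is real and should be corrected. The withdrawal sections run the trial per protocol while section 9.3 analyses it as randomised. For laboratory, hypotension and pregnancy withdrawals, the outcomes that 9.3 needs are expressly not collected. For non-compliance the text orders withdrawal and replacement, but the sentence in 13.1 that ends data collection follows on from the other three routes.

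The cost of one laboratory withdrawal is 4 to 6 of 6 primary Aim 2 measurements and 46 to 50 of 52 weeks of recurrence follow-up, for a tenth of one arm. This rests on the Table 1 schedule and on withdrawal at a scheduled draw.

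Two stronger conclusions are not supported. A reader might infer that the effect estimates will be biased by a material amount. The documents give no abnormality rate and no link between a laboratory value and hamstring outcome, so bias is possible but of unknown size. A reader might also infer that withdrawn subjects are left without safety care. Sections 8.4 and 13.1 continue clinical follow-up, and 8.4 includes blood work 4 to 6 weeks after stopping the drug. What is lost is research outcomes and scheduled event questioning.

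**What to change.** Amend sections 5.1.1, 8.4 and 13.1 together, since any one left unchanged would contradict the others:

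- State that non-compliance, symptomatic hypotension, a clinically relevant laboratory abnormality or pregnancy stops study drug only.
- Keep the subject in the Table 1 safety and outcome visits that remain clinically appropriate, and in the as-randomised set of section 9.3.
- State that any replacement is added to that set and does not take the withdrawn subject's place in it.
- State that an abnormal value found after dosing has ended is recorded and followed, and does not end participation.
- Delete the per-protocol declaration from 5.1.1 and 13.1, leaving per protocol as the secondary analysis in 9.3.

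The cost is wording in three sections and matching consent text. Affected subjects complete visits that are already scheduled, and there is less need to recruit replacements. Safety care is unchanged.
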